6.1.1 Anti-tumor Treatment

Standard and experimental anti-tumor therapies are permitted.

6.1.2 Supportive Care

- a. Dexamethasone should be used in the smallest dose to control symptoms of cerebral edema and mass effect, and discontinued if possible. Prednisone is not permitted because it induces CYP2C19.
- b. Febrile neutropenia may be managed according to the local institution's Infectious Disease guidelines. Measures may include appropriate laboratory testing, including blood and urine cultures and the institution of broad-spectrum antibiotics. If a source for the fever is not identified or the fever resolves when the neutrophil count recovers, antibiotics may be discontinued and the patient observed.
- c. The use of antiemetics will be left to the investigators' discretion.

d. Other Concomitant Medications

Therapies considered necessary for the wellbeing of the patient may be given at the discretion of the investigator. Other concomitant medications should be avoided except for analgesics, chronic treatments for concomitant medical conditions, or agents required for life-threatening medical problems. No other anti-convulsant medication are allowed while on the study. All concomitant medications must be recorded.

f. Surgery

If neurosurgical management is required for any reason, the procedure must be documented, including the indications for surgery, the surgical operative note and pathology report.

6.1.3 Definition of dose limiting toxicities (DLT):

Toxicities will be graded according to the NCI Common Terminology Criteria for Adverse Events (CTCAE) version 4.0. If multiple toxicities are seen, the presence of DLT should be based on the most severe toxicity experienced. DLT will be defined as any grade 3 toxicity that:

- Is not amenable to maximal medical management, and
- Is attributable to the study drug, and
- Occurs during treatment with lacosamide or placebo.

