6.2.1.2 Agent Administration

Lacosamide and placebo will be taken by mouth twice a day, at approximately the same times each day, spaced as close to 12 hours apart as possible. Medication may be taken with or without food. Missed doses should be taken so long as the dose will be taken within 6 hours of the scheduled time. Vomited doses will not be retaken unless the pill can be clearly identified in the vomitus. Patients will be given drug diaries every 3 months to monitor compliance (see Appendix 17.5).

6.2.1.3 Registration/Randomization:

See Section 15.3.2 for registration/randomization procedures.

6.2.1.4 Drug Dose/s and Treatment Schedule:

Patients may be taking peri-operative AEDs at the time of registration. These agents should be tapered off (on the investigator's preferred schedule) over 1-2 weeks. Lacosamide or placebo will be initiated at the same time that the taper commences. The starting dose of lacosamide or placebo will be 50 mg PO bid. Over 4 weeks, the dose should be increased to a target dose of 200 mg bid. A recommended scheme for dose escalation is to increase by 100 mg/day weekly until 200 mg bid is achieved. Deviations from this scheme that achieve a dose of 200 mg bid by 4 weeks will not be considered protocol violations.

6.3 Dose Modifications:

Patients who experience a treatment-related DLT as defined in Section 6.1.3 should have clinical evaluations and/or laboratory testing at appropriate intervals until the toxicity has resolved.

If a patient experiences DLT, the dose may be reduced or the treatment suspended, at the discretion of the treating investigator. Continuing therapy at a reduced dose should be seriously considered because of the risk of seizure associated with sudden cessation of any AED.

Doses between 50 mg bid and 200 mg bid are permissible during the study, and adjustments may be made as deemed appropriate by the investigator. However, every effort should be made to maintain the target dose of 200 mg bid whenever possible.

If a patient experiences DLT at a dose of 50 mg bid, the treatment should be discontinued.

Doses that are reduced for lacosamide or placebo-related toxicity may be re-escalated to the original dose level, if in the opinion of the treating investigator, it is safe to do so.

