Treatment may be held for up to 4 weeks, at the investigator's discretion. If the toxicity does not resolve to a level at which the investigator feels comfortable resuming study drug within 4 weeks, or if a patient experiences DLT at a dose of 50 mg bid, the treatment should be permanently discontinued.

For treatment or dose modification related questions, please contact the Study Chair or the MDACC OMCR at UT MDACC at [contact] or [contact].

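### Dose-limiting toxicity is defined as grade 3 with no 'or higher', so read literally a refractory, drug-attributable grade 4 event is not a DLT and does not trigger the DLT rules in Section 6.3

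*Combined protocol and SAP*

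**What the plan says.** Section 6.1.3 grades toxicity by CTCAE version 4.0. It then says "DLT will be defined as any grade 3 toxicity that" meets three joint conditions: it cannot be controlled by full medical management, it is attributed to study drug, and it arises on lacosamide or placebo. For a patient with several toxicities, "the presence of DLT should be based on the most severe toxicity experienced".

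Section 6.3 takes up that definition by number. Patients with a DLT "should have clinical evaluations and/or laboratory testing at appropriate intervals until the toxicity has resolved". The dose may be reduced or treatment suspended at the investigator's discretion. At the lowest dose the rule is firmer: "If a patient experiences DLT at a dose of 50 mg bid, the treatment should be discontinued". The same rule is repeated later in Section 6.3: "or if a patient experiences DLT at a dose of 50 mg bid, the treatment should be permanently discontinued". The permitted range is set by "Doses between 50 mg bid and 200 mg bid are permissible during the study", so no reduction is available below 50 mg bid.

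Two parts of Section 6.3 do not depend on a DLT or on grade. The investigator may adjust the dose within the permitted range, with an aim of keeping patients at target. In addition, "Treatment may be held for up to 4 weeks", and a toxicity that has not settled enough in that time leads to a permanent stop.

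Section 10.1(b) lists unacceptable toxicity as a reason for removal and refers the reader to Section 6.1.3.

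**The concern.** A severity threshold in a dosing rule normally works as a floor: whatever applies to a grade 3 event applies at least as strongly to grade 4. Section 6.1.3 names one grade and no range. Taken at its word, it gives a refractory, drug-attributable grade 3 event at 50 mg bid an instruction to discontinue, while the same kind of event at grade 4 gets no such instruction from that rule. The instruction to follow the toxicity until it resolves is lost in the same way, at any dose.

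What is at stake is patient safety and uniform conduct across sites in a multicenter trial. The rule should not depend on each site supplying a missing phrase. Nothing in the efficacy analysis is at stake.

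**Working it through.** No arithmetic applies, because the plan gives no figure on this point. The check sets the provisions side by side for one case: an event that is refractory, attributable and on treatment, first at grade 3 and then at grade 4.

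1. **Is it a DLT (6.1.3)?** Grade 3: yes. Grade 4: no, on the literal wording. The protocol writes ranges and floors elsewhere when it means them. The reporting table in Section 15.7 separates grades 2 and 3, grades 1 to 3, and grades 4 and 5, and Section 4 uses ≥ for age and Karnofsky status. Section 6.1.3 uses neither device.

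2. **Does the multiple-toxicity sentence widen the definition?** No. It says which event decides when there are several. It makes sense only if worse events count at least as much as milder ones, so it is evidence that grade 3 was meant as a floor. It does not itself change the grade named in the definition.

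3. **What does 6.3 then direct?**

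| Provision | Grade 3 | Grade 4, literal reading |
|---|---|---|
| Follow-up until resolution (6.3) | Applies, as a DLT | Not triggered |
| Discontinuation at 50 mg bid (6.3, stated twice) | Applies, as a DLT | Not triggered |
| Investigator dose adjustment (6.3) | Available | Available |
| Hold of up to 4 weeks, then permanent stop if not settled (6.3) | Available | Available |
| Unacceptable toxicity (10.1(b)) | Covered | Covered or not, depending on how the cross-reference is read |
| Illness that in the investigator's judgment rules out further therapy (10.1(e)) | Available | Available |
| Off treatment if unblinded with a serious adverse event (15.12, step 10) | Available if unblinded | Available if unblinded |

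4. **What covers follow-up for grade 4?** Section 8.8 has adverse events evaluated at the monthly calls or visits, Section 8.1 allows laboratory tests at the investigator's discretion, and Section 15.6 has all adverse events recorded and followed as appropriate. These cover most of what the DLT follow-up sentence would add.

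5. **What does reporting add?** Section 15.7 is stricter for grade 4 than for grade 3: unexpected grade 4 events are phoned in within 24 hours regardless of attribution. That governs reporting and gives no dosing instruction.

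6. **Can the gap be sized?** No. Section 2.5 gives discontinuations for adverse events of 8% at 200 mg/day, 17% at 400 mg/day and 5% on placebo. It does not break them down by grade and gives nothing for 50 mg bid (2 × 50 = 100 mg/day). Section 3.12 gives frequency bands, also without grades.

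7. **Does it reach the analysis?** Section 11 has no DLT-based analysis and no DLT stopping boundary. Adverse events are summarised by worst grade whatever the DLT status (Section 11.2.5). The power calculation, the interim boundary and the primary test do not use DLT.

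**The case against.** The strongest reply is that any clinician would read grade 3 as a minimum, and that several other routes lead to a stop. Much of this stands.

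- **Section 10.1(b).** It says *see* Section 6.1.3, whereas the next line, on seizure, and Section 6.3 use *as defined in*. Section 6.1.3 never uses the term unacceptable toxicity. On ordinary meaning, a refractory, drug-attributable grade 4 event is unacceptable toxicity and meets a listed removal criterion. This reading is open, and it narrows the gap.
- **Discretion.** Dose adjustment, the hold, the 4-week limit and Section 10.1(e) are open at any grade. Section 15.12 adds a route through unblinding, although the investigator only may request it and approval is needed. An investigator would very likely stop the drug.

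Three stronger readings are tempting, and the documents do not support them.

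- A reader might infer that grade 3 gets an instant, mandatory stop and grade 4 gets none. Section 6.3 says treatment *should* be discontinued and gives no timing. The grade 3 rule itself rests on judgments of attribution and of failed management.
- A reader might infer from the multiple-toxicity sentence that a grade 4 event cancels a grade 3 DLT in the same patient. That is a strained reading of a sentence whose evident purpose is to let the worst event govern.
- A reader might infer that the gap is confined to 50 mg bid, and so to a short first step, since "A recommended scheme for dose escalation is to increase by 100 mg/day weekly until 200 mg bid is achieved". That is scheduled time under a recommended scheme, not a measure of risk, and patients may later be reduced to that dose. The DLT follow-up instruction applies at every dose. If Section 10.1(b) does adopt the DLT definition exclusively, the difference in removal criteria is not limited to one dose either.

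What survives the reply is the wording itself: no section widens the definition, and the 50 mg bid rule applies only to a DLT.

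**Conclusion.** The definition is wrong as written, and the point is minor. On the literal text, a refractory, attributable grade 4 event on treatment is not a DLT, so it triggers neither the DLT-directed follow-up nor the 50 mg bid discontinuation rule, while a grade 3 event triggers both. The likely cause is an omitted phrase rather than a deliberate choice.

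The conclusion assumes only that *grade 3* means grade 3 and not grade 3 and above. It does not assume that Section 10.1(b) excludes grade 4, and it does not say that such a patient would be left on drug. Practical risk is low, and no count of patients can be given. The endpoint, power and alpha do not change.

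**What to change.** In Section 6.1.3, change *any grade 3 toxicity* to *any grade 3 or higher toxicity*. Section 6.3 refers to the Section 6.1.3 definition, so its follow-up and 50 mg bid rules then apply to grade 4 without further edits there.

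The cost is two added words at the next amendment, with no change to sample size, analysis or data collection.

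The edit does not settle how Section 10.1(b) should be read. If unacceptable toxicity there means exactly a DLT, any DLT at any dose meets a removal criterion. That sits awkwardly with the advice in Section 6.3 to consider continuing at a reduced dose. The sponsor may wish to clarify that separately.

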6.2 Treatment Plan

6.2.1 All Patients

6.2.1.1 Evaluations During Treatment

The evaluations required for all patients include medical history, physical and neurologic examinations, electroencephalograms (EEGs; optional), electrocardiogram (EKG; at screening only), MD Anderson Symptom Inventory-Brain Tumor Module (MDASI-BT), Karnofsky Performance Status (KPS), and laboratory tests (at screening only). The schedule of evaluations is provided in Sections 7 and 8.

6.2.1.2 Agent Administration

Lacosamide and placebo will be taken by mouth twice a day, at approximately the same times each day, spaced as close to 12 hours apart as possible. Medication may be taken with or without food. Missed doses should be taken so long as the dose will be taken within 6 hours of the scheduled time. Vomited doses will not be retaken unless the pill can be clearly identified in the vomitus. Patients will be given drug diaries every 3 months to monitor compliance (see Appendix 17.5).

6.2.1.3 Registration/Randomization:

See Section 15.3.2 for registration/randomization procedures.

6.2.1.4 Drug Dose/s and Treatment Schedule:

Patients may be taking peri-operative AEDs at the time of registration. These agents should be tapered off (on the investigator's preferred schedule) over 1-2 weeks. Lacosamide or placebo will be initiated at the same time that the taper commences. The starting dose of lacosamide or placebo will be 50 mg PO bid. Over 4 weeks, the dose should be increased to a target dose of 200 mg bid. A recommended scheme for dose escalation is to increase by 100 mg/day weekly until 200 mg bid is achieved. Deviations from this scheme that achieve a dose of 200 mg bid by 4 weeks will not be considered protocol violations.

6.3 Dose Modifications:

Patients who experience a treatment-related DLT as defined in Section 6.1.3 should have clinical evaluations and/or laboratory testing at appropriate intervals until the toxicity has resolved.

If a patient experiences DLT, the dose may be reduced or the treatment suspended, at the discretion of the treating investigator. Continuing therapy at a reduced dose should be seriously considered because of the risk of seizure associated with sudden cessation of any AED.

Doses between 50 mg bid and 200 mg bid are permissible during the study, and adjustments may be made as deemed appropriate by the investigator. However, every effort should be made to maintain the target dose of 200 mg bid whenever possible.

If a patient experiences DLT at a dose of 50 mg bid, the treatment should be discontinued.

Doses that are reduced for lacosamide or placebo-related toxicity may be re-escalated to the original dose level, if in the opinion of the treating investigator, it is safe to do so.

Treatment may be held for up to 4 weeks, at the investigator's discretion. If the toxicity does not resolve to a level at which the investigator feels comfortable resuming study drug within 4 weeks, or if a patient experiences DLT at a dose of 50 mg bid, the treatment should be permanently discontinued.

For treatment or dose modification related questions, please contact the Study Chair or the MDACC OMCR at UT MDACC at [contact] or [contact].

7.0 PRETREATMENT EVALUATION

General Requirements

Unless otherwise noted, all pretreatment evaluations must be performed within 14 days prior to the registration. A model study calendar is presented in Figure 8-1.

- 7.1 A complete history and neurological examination (to include demographic information, vital signs, and documentation of the Karnofsky Performance Status per Appendix 17.2) shall be performed on all patients.
- 7.2 Prestudy laboratory tests shall include CBC, differential, platelets, sodium, potassium, bicarbonate, chloride, BUN, serum creatinine, glucose, bilirubin, SGOT, SGPT, alkaline phosphatase, and serum pregnancy test for women of childbearing potential. Patients must agree to practice adequate contraception. The treating physician should use their own discretion regarding how long patient should continue contraception use after discontinuing treatment.
- 7.3 Documentation of tumor diagnosis.
- 7.4 Patients will complete a baseline MDASI-BT (Appendix 17.3) prior to the first dose of study medication at the doctor's office or clinic. At this time the MDASI-BT will be completed only by the patient, unless changes in vision or weakness make this difficult. If this occurs, then the caregiver nurse may read the questions to the patient or assist with marking the severity number or score as described by the patient.
- 7.5 EKG. Required to evaluate PR interval for eligibility.
- 7.6 EEG (optional but should be obtained whenever possible).

8.0 EVALUATION DURING STUDY

General Requirements

Unless otherwise noted, all evaluations may be performed within 14 days before the scheduled date. A model study calendar is presented in Figure 8-1.

- 8.1 Laboratory tests will be obtained only as deemed necessary by the investigator during study treatment.
- 8.2 All relevant information regarding drugs, doses, laboratory examinations, and treatment-related toxicities shall be documented in the patient's medical record and flow sheets.
- 8.3 A complete history and neurologic exam (to include vital signs and documentation of the patient's Karnofsky Performance Status) will be performed at least every 3 months, +/-2 weeks.
- 8.4 Every 4 weeks when the patient is not seen by the study team, telephone contact between the patient and a study clinician (nurse or MD) is required to assess for possible seizure in the preceding month.. The Site to complete the BTTC 11-01 Interim Telephone Contact Checklistform . Calls or visits must occur on the scheduled date or within 2 weeks prior to the scheduled date.
- 8.5 *EEG should be obtained whenever possible to confirm the clinical impression of seizure.* Because the diagnosis of seizure is frequently made by history, this test is optional.
- 8.6 All patients will be followed for overall survival at least every 3 months, when possible. The follow up will continue until 5 years after the End of Study visit. The follow up can take place via telephone contact by the nurse, study coordinator, or MD.
- 8.7 The MDASI-BT (Appendix 17.3) will be administered every 4 weeks in clinic or by telephone *ONLY* by the nurse or MD.
- 8.8 All patients will be evaluated for adverse events at the monthly telephone calls or visits. In addition all serious adverse events will be reported to the OMCR and the study chair as directed in section 15.7.

Figure 8-1. Model Study Calendar.

	Screening	Start of treatment Visit 1^c (Day 1 of Month 1)	On-treatment period Visits 2-4^c (Day 1 of Months 4, 7, 10)	Last treatment visit Visit 5^c (Day 1 of Month 13)
Demographic data	X			
Drug dispensing/return		X	X	X
Re-Order Drug			X^e	
MDASI-BT ^a		X	X	X
Karnofsky Performance Status	X	X	X	X
EKG ^b	X			
Lab tests ^b	X	X		
EEG ^d	X			
Medical and seizure history	X	X	X	X
Physical and neurologic examination	X	X	X	X
Randomization		X		
Recording of adverse events ^a			X	X
Verification of inclusion/ exclusion criteria	X			
Vital signs	X	X	X	X
Written informed consent	X			
Long Term Follow Up	Phone call for survival data every 3 months for 5 years from initial diagnosis date			

- ^a Every 4 weeks by telephone call while on treatment.
- ^b At baseline and then only as clinically indicated (CBC, differential, platelets, sodium, potassium, bicarbonate, chloride, BUN, serum creatinine, glucose, bilirubin, SGOT, SGPT, alkaline phosphatase, serum pregnancy test for women of childbearing potential, and AED levels if appropriate).
- ^c All required evaluations may be performed within 14 days before the scheduled date, except where otherwise noted.
- ^d EEG should be obtained at baseline and to confirm the clinical impression of seizure. Because the diagnosis of seizure is frequently made by history, this test is optional (at both timepoints).
- ^e Reorder drug after phone contact on months 2, 5 and, 8 between visits provided the patient has not experienced a seizure.

9.0 CRITERIA FOR EVALUATION AND ENDPOINT DEFINITIONS

9.1 Definition of Seizure

Patients and caregivers will be educated about signs and symptoms of seizures using a standard education sheet (Appendix 17.5). They will be instructed to contact the investigator immediately for possible seizure activity. For study purposes, confirmed seizures will include any of the following:

1. Simple partial seizures:
 - a) with motor symptoms: focal motor movements, versive/postural movements
 - b) with sensory symptoms: olfactory sensations
 - c) with autonomic signs
 - d) with psychic symptoms (sudden reversible loss of expressive/receptive speech)
2. Complex partial seizures
 - a) with impairment of consciousness only
 - b) with impairment of consciousness plus automatisms (lip smacking, fumbling, etc)
3. Partial seizures with secondarily generalized seizures
 - a) Unconsciousness with myoclonic jerks with or without tongue-bite or stiffening
 - b) Unconsciousness with tonic spasm, without myoclonic jerks, with or without tongue-bite
 - c) Unconsciousness with tongue-bite without myoclonic jerks or stiffening
 - d) Unconsciousness or staring with one of the following preceding symptoms perceived by the patient:
 - A rising feeling from the abdomen to the throat
 - Smelling of odd scents
 - Stiffening or convulsions in the face or limb(s)
 - Turning the head to one side

Excluded attacks are those deemed by the treating physician to be non-neurologic in origin and are comprised of:

- Merely staring
- Exclusively unconscious with or without incontinence for urine
- Solely disturbances of seeing, feeling, or thinking

9.2 Clinical Event Committee

Medical records from the first post-event physician visit and other relevant medical record information will be forwarded to a blinded “clinical event committee” (CEC) that will review source documents and classify events as seizures or otherwise. The study investigators and the CEC will be instructed to utilize a standard seizure definition (Section 9.1). The committee will be composed of board-certified neurologists who have no other involvement with the study. Each event will be adjudicated by 2 independent reviewers. If the reviewers do not agree about the nature of the event, a third

independent reviewer will adjudicate the event. Additional details regarding the clinical event committee are presented in the Clinical Event Committee Charter.

9.3 Patient Reported Outcomes

This study seeks to establish whether the use of the AED lacosamide reduces the occurrence of seizures. However, given the potential side effects and symptoms associated with both seizures and the use of AEDs, it will be important to determine whether if any determined benefit is associated with improvements in symptoms and the interference of symptoms with daily life or does a worsening of these parameters offset the benefit.

Precedence for measuring “non-therapeutic” endpoints exists in oncology research. For example, gemcitabine was approved by the FDA partially as a consequence of the decrease in pain reported in pancreatic patients who were treated, not on the basis of survival improvement which was modest, at best [32]. There have been efforts in neuro-oncology to evaluate secondary endpoints using validated instruments as additional indicators of benefit.

The M.D. Anderson Symptom Inventory-Brain Tumor Module (MDASI-BT) allows the self-reporting of symptom severity and interference with daily activities. The MDASI-BT has demonstrated reliability and validity in the adult primary brain tumor patient population [33]. This tool represents a modification of the widely used and validated MDASI, with particular attention to symptoms common in patients with brain tumors. The availability of validated instruments provides an opportunity to prospectively assess the impact of treatment, both positive and negative, on patients. This evaluation of symptom burden in this study will assist in finding the best possible treatment with the least toxicity.

